Many (e-Health) initiatives arose focussing on physical activity in CVD patients, but in general it sorted only into small-to-medium effects that are not sustained over time and the more effective interventions are complex and therefore difficult to implement in routine care.²⁵⁻²⁷ Intervention studies targeting SB in CVD patients are scarce. To address this gap, we developed an in-person delivered intervention integrated in routine care with an add-on e-health component to prompt and monitor behaviour change. This intervention was co-created together with both patients and health care professionals (HCPs) and adapted to fit with restrictions and opportunities in routine care. In this study we investigated the effect of the '*Sitting Interruption Treatment as a personaliZEd Secondary prevention Strategy*' (SIT LESS) intervention on SB in patients with coronary artery disease directly after CR and after 6 months of follow-up. This study showed that enrichment of CR with a tailored sedentary behavior intervention induces greater reductions in ST compared to usual care²⁸. However, these beneficial lifestyle adaptations were only temporary²⁸ as sustainable PA habits after CR remain challenging^{29,30}.

E-Health programs could support patients to maintain beneficial PA levels following CR²⁹. Moreover, short, remote Booster programs may already nudge CR graduates towards a more physically active lifestyle³¹. Such Booster programs should include continued support to allow self-monitoring of behavior, goal-setting and associated feedback²⁹. However, the effect of a remote eHealth-based Booster program aiming to reducing ST in patients with CAD is currently unknown. Therefore, the

effects of SIT LESS Booster sessions on SB will be examined among patients who participated in the SIT LESS group ~2 years ago.

4. Objectives

The primary objective is to examine the effectiveness of a remote 3-week Booster behavior intervention compared to usual care on reducing ST.

[figure not shown]
Secondary objectives are:

- a) To examine the effectiveness of a remote 3-week Booster behavior intervention compared to usual care on improving sedentary behavior defined as number of prolonged sedentary bouts and prevalence of a ST ≥ 9.5 h/day.
- b) To examine the effectiveness of a remote 3-week Booster behavior intervention compared to usual care on improving physical activity characteristics.

5. Trial design

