A parallel-group randomized controlled trial will be conducted to determine the effectiveness of a 3-week, fully-remote and personalized behavior change intervention (Booster intervention) with a primary focus on reducing and interrupting ST in patients with CAD. The Booster is a compressed version of the SIT LESS intervention, which has previously been described in detail³². Participants who received the original SIT LESS intervention during their CR program (1.5 to 2.5 years ago) and of which accelerometry-based ST and PA characteristics were derived will be approached for this study at the end of August 2023. After inclusion, baseline characteristics are gathered including the same assessment of ST and PA characteristics by an accelerometer send by mail (**Figure 1**). Following baseline measurements, participants are randomly assigned into the control or Booster group. The control groups received usual care, where the Booster group additionally receives the Booster intervention. Finally, the accelerometry measurement are repeated in both groups at the end of the Booster intervention (post-intervention). Our trial is approved by the Medical Ethics Committee of the Radboud university medical center (NL72604.091.20), is in accordance with the principles of the Declaration of Helsinki and all participants will give written informed consent.

Randomization will occur after the completion of all baseline assessments using a computerized algorithm (Castor Electronic Data Capture 2021, Ciwit B.V., Amsterdam, The Netherlands).

**Figure 1.** SIT LESS (transparent) and BOOSTSITLESS randomized controlled trial flowchart.

CR: Cardiac Rehabilitation; SIT LESS, Sedentary Behavior Intervention as a Personalized Secondary Prevention Strategy

6. Disease condition and selection of patients

Eligible patients are defined on the inclusion and exclusion criteria. In general, patients with coronary artery disease who followed cardiac rehabilitation with a special sedentary reduction program (SIT LESS). Specific inclusion and exclusion criteria are:

Inclusion Criteria:

1. Participation in the SIT LESS intervention group of the original SIT LESS study. Inclusion criteria of the SIT LESS study were:
 - a. Patients aged \geq 18 years old
 - b. Referred to CR because of stable CAD, an acute coronary syndrome, and/or after coronary revascularization.

Exclusion Criteria:

1. Unable to give informed consent
2. Wheelchair-bounded / not physically able to stand or walk.

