### 3.7 Timing of outcome assessment

The primary and secondary outcomes will be assessed at baseline and post intervention (3 weeks).

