#### 5.2 Eligibility

Eligible patients were defined on the inclusion and exclusion criteria. In general, patients with coronary artery disease who followed cardiac rehabilitation with a special sedentary reduction program (SIT LESS) were included. Specific inclusion and exclusion criteria are:

Inclusion Criteria:

1. Participation in the SIT LESS intervention group of the original SIT LESS study. Inclusion criteria of the SIT LESS study were:
  - a. Patients aged  $\geq 18$  years old
  - b. Referred to CR because of stable CAD, an acute coronary syndrome, and/or after coronary revascularization.

Exclusion Criteria:

1. Unable to give informed consent.
2. Wheelchair-bounded / not physically able to stand or walk.
3. Dutch Language barrier.
4. Coronary arterial bypass graft surgery expected within 8 weeks after inclusion.
5. New York Heart Association class III or IV heart failure.
6. Participation in another interventional study targeting sedentary behavior or physical activity.

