#### 5.3 Recruitment

A CONSORT flow diagram will be used to summarize the number of patients who were:

---

- Eligible for study participation based on participation in the SIT LESS study without dropping out.
- Approached for study participation (Reasons for no approach will be given\*).
- Included in the study.
- Randomized.
- Received the randomized allocation .
- Did not receive the randomized allocation\*.
- Lost to follow-up\*.
- Discontinued the intervention\*.
- Randomized and included in the primary analysis.
- Randomized and excluded from the primary analysis\*.

\*reasons will be provided

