## 6.4 Additional analyses

To assess the presence of potential selection bias among study participants, sedentary behavior and physical activity characteristics at 3 months post-CR (i.e. last assessment of previous RCT) will be compared between our analytical cohort and non-participants using an independent samples t-test (continuous normally distributed data), Wilcoxon-signed rank test (continuous not-normally distributed data) or  $\chi^2$  test (categorical data).

To assess the long-term effects of CR on sedentary behavior and PA characteristics taking into account the results of the original SITLESS, linear (continuous data) and logistic (categorical data) mixed-model analyses with time as a categorical variable will be used. The BOOSTSITLESS is taken as reference and compared to measurements at pre-CR, post-CR and 3 months post-CR measurements of the previous (SITLESS) RCT.

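### SAP 6.4 labels an uncontrolled change over time as the long-term effects of CR, although every participant had CR plus SIT LESS and there is no comparison group

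*SAP*

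**What the plan says.** The second analysis in SAP 6.4 has the aim "To assess the long-term effects of CR on sedentary behavior and PA characteristics", taking the original SIT LESS results into account. On method it says that linear and logistic "mixed-model analyses with time as a categorical variable will be used". On the contrast it says: "The BOOSTSITLESS is taken as reference and compared to measurements at pre-CR, post-CR and 3 months post-CR measurements" of the previous trial. It names no group or CR-exposure term, and does not say which BOOSTSITLESS visit is the reference or whose SIT LESS records enter the model.

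Other sections bear on this:

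- **Who is in the cohort.** The inclusion criterion in SAP 5.2 is "Participation in the SIT LESS intervention group of the original SIT LESS study". The flow diagram in SAP 5.3 starts from people "Eligible for study participation based on participation in the SIT LESS study without dropping out".
- **What SIT LESS did.** Protocol section 3 reports that "enrichment of CR with a tailored sedentary behavior intervention induces greater reductions in ST compared to usual care".
- **Which visits exist.** SAP 3.7 gives two, baseline and 3 weeks. Protocol section 5 fixes their order: "Following baseline measurements, participants are randomly assigned into the control or Booster group".
- **Selection.** The first analysis in SAP 6.4 compares participants with non-participants at 3 months post-CR.
- **Missing data.** SAP 6.3 expects to assume missing at random and to rely on the mixed model.

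**The concern.** An effect of CR is a contrast between what happened with CR and what would have happened without it. The planned model contrasts the same kind of patient at different times, all after referral to CR and all allocated to SIT LESS. Anything else that changes over about two years falls into the same estimate.

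The label matters because relapse after CR is the trial's rationale (Protocol sections 2 and 3). A result headed as a long-term effect of CR is likely to be read as evidence on how durable CR is, in either direction, and the design cannot supply that.

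Two unspecified details affect the estimate even when it is read as description: which BOOSTSITLESS visit is the reference, and whether the earlier records of SIT LESS-arm patients who did not join BOOSTSITLESS are used.

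**Working it through.** SAP 6.4 gives no figure to reproduce. Step 1 is reasoning from the text; steps 2 to 4 are illustrations.

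**1. What the contrast can identify.** Set the aim in SAP 6.4 beside the eligibility rule in SAP 5.2 and the SIT LESS result in Protocol section 3.

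- No CR: nobody in the cohort.
- CR without SIT LESS: nobody in the cohort. Usual-care patients of the original trial are not eligible, so this plan gives them no two-year measurement.
- CR plus SIT LESS: everybody.

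On the protocol's own account SIT LESS changed ST beyond usual care, so the course over time contains at least CR and SIT LESS together. Time since the event, season and ageing are added to it. A time factor alone cannot separate these.

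**2. What naming the reference visit settles.** With 1:1 allocation (SAP 3.2), half the cohort has been allocated to Booster by the 3-week visit.

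Shift in reference mean = Booster effect × 1/2 × share of reference records that are post-intervention.

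- Baseline only: share 0, shift 0.
- Both visits pooled: share 1/2, shift one quarter of the Booster effect.
- Post-intervention only: share 1, shift one half of it.

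Taking the 0.3 SD of SAP 3.3 purely as an illustrative effect, the shifts are 0, 0.3 × 1/4 = 0.075 SD and 0.3 × 1/2 = 0.15 SD.

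**3. Regression to the mean if only participants are entered.** From SAP 3.3: 42 included, and 106 as the planned size of the SIT LESS arm. Assumed, because the documents give no figures: actual arm size about 106, ST SD 1.7 h/day, equal correlation r of 0.6 to 0.7 between all visits, participation depending on ST at 3 months post-CR, and no true change. Let d be the participant/non-participant difference at 3 months, in SD units.

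- Share participating: 42/106 = 0.396, so 1 − 0.396 = 0.604.
- Displacement of participants from the arm mean at 3 months: 0.604 × d × SD.
- Displacement at every other visit: r × 0.604 × d × SD.
- Spurious change from 3 months to BOOSTSITLESS: (1 − r) × 0.604 × d × SD.
- Spurious change from pre-CR or post-CR: (r − r) × 0.604 × d × SD = 0.

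With d = 0.5:

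- r = 0.7: 0.3 × 0.604 × 0.5 × 1.7 = 0.15 h/day.
- r = 0.6: 0.4 × 0.604 × 0.5 × 1.7 = 0.21 h/day (0.205 before rounding).

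Simulation with four equally correlated visits agrees: about 0.15 to 0.20 h/day from 3 months and about 0 from the two earlier visits. The sign follows the selection: a spurious rise if less sedentary patients join, a spurious fall if more sedentary patients do. A likelihood-based model on the whole arm gave a bias of about 0. Its standard error was similar under moderate selection and about 10 to 25% larger under strong selection.

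**4. What the planned selection check can do.** With 42 against 106 − 42 = 64, a two-sided t-test at 0.05 has these powers:

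| Difference (SD) | Power |
|---|---|
| 0.2 | 17% |
| 0.3 | 32% |
| 0.5 | 70% |
| 0.56 | about 80% |

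It would usually flag strong selection and often miss moderate selection. In neither case does it correct the estimate.

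**The case against.** The strongest reply is that this is a subsidiary analysis with a loosely worded aim. The objectives and hypothesis in SAP 2.2 make no claim about CR, and nothing in 6.4 feeds the treatment comparisons in 6.2. That stands, and it sets the priority. It does not rescue the label, which the design cannot deliver.

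A reader might infer four stronger things that the documents do not support.

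- *That the SAP draws an unsupported conclusion.* It states an aim; no conclusion is written.
- *That the reference is contaminated by Booster treatment.* Baseline precedes randomisation and is the natural two-year follow-up. Nothing says that the post-intervention visit is used or pooled. Step 2 sizes a missing detail, not an error.
- *That the model is restricted to the volunteers.* This is plausible but unstated. Selection is certain only at the BOOSTSITLESS time point, which only participants can supply.
- *That regression to the mean distorts every contrast.* Under equal correlations it affects the 3-month contrast only; the others would need unequal correlations.

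It can also be said that the SAP already checks for selection and that a whole-arm model answers a different question from change within participants. Both are true. The check examines only the step from SIT LESS to BOOSTSITLESS, at one visit. Either target population is legitimate, but the SAP should say which is meant.

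**Conclusion.** The concern holds as a matter of labelling. SAP 6.4 calls an uncontrolled change over time an effect of CR, in a cohort where everyone had CR plus SIT LESS. That rests only on the eligibility rule and the stated model, with no numerical assumption.

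The reference visit and the records to be entered are gaps in specification. The possible distortion from a participants-only model is roughly 0.15 to 0.20 h/day in the 3-month contrast. This is conditional on the assumed SD, the equal correlations, an arm of about 106, a 0.5 SD difference and participation that depends on ST at 3 months. Weaker selection would give less. The primary and secondary treatment comparisons are unaffected, and the priority is minor.

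**What to change.** Amend SAP 6.4 in one edit:

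1. Reword the aim, and any conclusion drawn from it, as *change over time since CR in SIT LESS-arm patients*, and drop the reference to effects of CR.
2. Name the pre-randomisation BOOSTSITLESS baseline visit as the reference.
3. Enter all SIT LESS-arm patients with any valid measurement in the mixed model, under the missing-at-random assumption of SAP 6.3, and state that the target is the whole arm.

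Items 1 and 2 cost only wording. Item 3 should need no new data collection: the planned selection check already presupposes non-participants' 3-month records. Its price is that the estimate describes the whole arm and not the participants, depends on missing at random, and has a standard error that is similar under moderate selection or about 10 to 25% larger under strong selection. The selection check should stay, as a description of who took part.

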## 6.5 Harms

The number and reasons of adverse events (e.g. falls, injuries, musculoskeletal problems, major cardiovascular disease events, and any other events potentially related to the implementation of the trial protocol) at each time point will be collected, reported, and described separately for each study arm. No formal statistical testing will be undertaken.

## 6.6 Statistical software

The analyses will be performed using R. For the main analyses we will use the 'lme4' or 'LMMstar' package. The use of packages will be reported in the manuscript.

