### 3.3 Sample Size

As our study has an explorative character, no formal sample size calculation was performed prior to trial initialization. For the original SIT LESS study, a sample size calculation was performed and described. Based on that calculation, 106 patients were needed in the SIT LESS arm of the trial. Participants in this study arm will be eligible for participation in the BOOSTSITLESS.

In the original SIT LESS study, we found an effect size Cohen D of 0.3 with an alpha of 0.05 and beta of 0.2 (power 0.8). The estimated sample size, based on previously mentioned parameters and repeated-measures ANOVA, needed for BOOSTSITLESS was 24 participants (12 in each study arm)(**Figure 2**) suggesting that the included sample size (n=42) is large enough to run meaningful analyses.

**Figure 2.** Sample size calculation using G\*power (version 3.1)

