## 4. Statistical principles

### 4.1 Confidence intervals and P values

All statistical tests will be two-tailed. P for significance will be set at 0.05 and 95% confidence intervals will be estimated.

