#### 4.3 Analysis populations

We plan to do an intention-to-treat analysis. This analytical cohort includes all randomized participants. With this approach, all randomized participants are included in the analysis, based on the groups to which they were initially randomly assigned. This imply that some participants will have valid data in both time points, while some might have missing data at baseline or post-intervention assessment.

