## 6.2 Analysis methods

The primary and secondary outcome analyses will be performed on an intention-to-treat basis using a constrained (i.e. baseline adjusted) linear mixed-model analysis to handle missing data and to avoid baseline imbalances between treatment arms. Time (categorical) and time\*group will be included in the model. In addition, we evaluate the difference between the control and Booster group in the proportion of participants with ST  $\geq 9.5$  h/day post-intervention by constrained logistic mixed model analysis.

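### Does leaving the primary mixed model open between lme4 and LMMstar, with no stated covariance structure or degrees-of-freedom method, put the 5% error rate at risk?

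*SAP*

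**What the plan says.** SAP 6.2 specifies the primary analysis as an intention-to-treat "constrained (i.e. baseline adjusted) linear mixed-model analysis to handle missing data and to avoid baseline imbalances between treatment arms". It lists the fixed part: "Time (categorical) and time\*group will be included in the model". SAP 3.7 sets two assessments, baseline and 3 weeks.

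On software, SAP 6.6 states "For the main analyses we will use the 'lme4' or 'LMMstar' package" and adds "The use of packages will be reported in the manuscript".

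On inference, SAP 4.1 makes all tests two-tailed and states "P for significance will be set at 0.05 and 95% confidence intervals will be estimated". SAP 3.3 gives the included sample as 42. SAP 4.3 keeps every randomised participant in the analysis and accepts that "some might have missing data at baseline or post-intervention assessment".

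Protocol section 9 names baseline constrained mixed models and refers to the SAP for detail. Neither document mentions random effects, a residual covariance, REML or ML, or a degrees-of-freedom method. Neither gives an SD of ST at either visit or a between-visit correlation.

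**The concern.** Naming a package does not fix a model. In lme4 the habitual fit for two visits is a random intercept with a single residual variance, which forces the baseline and post-intervention variances to be equal. LMMstar, the other named option, lends itself to an unstructured 2x2 covariance with a separate variance at each visit. The two fits can give different standard errors and p-values from the same data.

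The baseline constraint makes this matter. With a common baseline mean, the treatment estimate is the post-intervention difference adjusted for the baseline difference, so its standard error depends on the post-intervention variance. If ST became more variable after the intervention, a pooled variance would understate that standard error. If it became less variable, the pooled variance would overstate it. With 42 participants, a superiority test at 0.05 and a package to be reported only in the manuscript, it is fair to ask whether the primary p-value could turn on a choice made after the data are in.

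**Working it through.** The plan has no figure of its own on this point to reproduce. The check asks how far a random-intercept fit would stray from 5%, and under what conditions.

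**Inputs.** From the SAP: 42 participants (3.3), 1:1 allocation (3.2), taken as 21 per arm; two visits (3.7); two-sided 0.05 (4.1). Assumed, because the documents are silent: the ratio k of post-intervention to baseline SD, from 0.8 to 1.4, and the between-visit correlation ρ, from 0.5 to 0.8.

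**Same SD change in both arms (large sample, complete data).** Set the baseline SD to 1.

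- The random intercept pools the variances to V = (1+k²)/2 and uses the slope b = 2ρk/(1+k²).
- Model variance, per unit: V(1−b²) = [(1+k²)/2]·[1 − 4ρ²k²/(1+k²)²].
- True variance: k² − 2bρk + b² = k²·[1 − 4ρ²k²/(1+k²)²].
- True/model = 2k²/(1+k²), in which ρ cancels.
- Type I error = 2·[1 − Φ(1.96/√ratio)].

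| k, both arms | True/model variance | 1.96/√ratio | Type I error |
|---|---|---|---|
| 0.8 | 1.28/1.64 = 0.780 | 2.219 | 2.7% |
| 1.0 | 1.000 | 1.960 | 5.0% |
| 1.1 | 2.42/2.21 = 1.095 | 1.873 | 6.1% |
| 1.2 | 2.88/2.44 = 1.180 | 1.804 | 7.1% |
| 1.4 | 3.92/2.96 = 1.324 | 1.703 | 8.9% |

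**SD change in the Booster arm only (1.2 times, ρ = 0.6).**

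- Mean post variance = (1+1.44)/2 = 1.22, so V = (1+1.22)/2 = 1.11.
- Mean covariance = 0.6·(1+1.2)/2 = 0.66, so b = 0.66/1.11 = 0.5946.
- Model variance = 1.11·(1−0.3535) = 0.7176.
- True variance, averaged over arms = (0.6400 + 0.9373)/2 = 0.7887.
- Ratio = 1.099, and 1.96/√1.099 = 1.870, giving 6.2%.

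**Simulation at the trial's size** (10,000 null trials per scenario, 21 per arm, ρ = 0.6, REML, Satterthwaite degrees of freedom; Monte Carlo SE 0.2 to 0.3 points).

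| Scenario | Random intercept | Unstructured |
|---|---|---|
| Equal SDs | 5.3% | 5.4% |
| Both arms 1.1 | 6.4% | 5.4% |
| Both arms 1.2 | 7.2% | 5.4% |
| Both arms 1.4 | 9.3% | 5.4% |
| Both arms 0.8 | 3.0% | 5.4% |
| Booster only 1.2 | 6.4% | 5.6% |
| Booster only 0.8 | 4.1% | 5.4% |

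A separate simulation at ρ = 0.7 gave 5.4% at equal SDs, 7.4% at 1.25 times and 3.2% at 0.8 times (both arms), which agrees. With 4 of 42 post values missing completely at random, the random intercept gave 5.5% at equal SDs and 7.6% at 1.2 times in both arms; the unstructured model gave 5.6% in both cases.

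**Degrees of freedom.** At equal SDs the random intercept rejects at 5.3% with Satterthwaite and 5.1% with t on 39 degrees of freedom. A normal reference gives about 6% in the ρ = 0.5 to 0.8 runs. Between the two t references the choice is close to immaterial.

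**Cost of visit-specific variances.** At equal SDs the SD of the estimate is 0.2502 against 0.2492, a ratio of 1.004. An analyst who frees the variance loses almost nothing.

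**The case for a change.** The strongest case for a change is that the mechanism is exact algebra, three sets of simulations agree with it, and stating the covariance would cost one sentence and one variance parameter. The trial's exploratory character is no answer, since the SAP commits to a superiority test at 0.05 with 95% intervals, and a wrong standard error spoils the interval too. Nor is the mixed model's handling of missing data an answer, because the departure persists with missing post values.

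All of that stands as a description of what a poor choice could do. It does not show that the plan makes that choice:

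- No section mentions a random intercept. That is a guess at what an analyst would type.
- The larger figures need the SD to rise in both arms. A ratio of 1.2 to 1.4 means variance growing by 44% to 96% (1.2² = 1.44, 1.4² = 1.96) in controls too. They receive only usual care and are measured with the same device and 8-day wear protocol, 3 weeks apart. Nothing in the documents points to this. A change confined to the Booster arm is easier to imagine, and there a ratio of 1.2 gives about 6%.
- A fall in SD makes the test conservative, which costs power and does not inflate false positives.
- Keeping lme4 and adding a post-visit random effect is not an equivalent repair. That term can only raise the post variance above baseline, so it does not help if ST becomes less variable. LMMstar avoids the difficulty and is already listed.

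One might also note that the fixed terms in SAP 6.2, typed literally in R, leave a free baseline difference between arms. The word constrained makes the intent clear. The literal coding would hold 5.0% to 5.1% and cost only precision, so it adds nothing here.

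**Conclusion.** The omission is genuine, but it is missing detail and not an error in the plan. The model class, the baseline constraint, the fixed terms, the population and the alpha are all given. What remains is the covariance and the reference distribution for a two-visit model. An analyst using the named LMMstar option with visit-specific variances and a t reference follows the SAP as written and holds 5.4% to 5.7% in every scenario simulated.

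The exposure is conditional on a random intercept that the SAP does not state and on SD ratios that the documents do not supply. On those assumptions the type I error is about 5% at equal SDs, about 6% at 1.2 times in the Booster arm only, about 7% at 1.2 times in both arms and about 3% at 0.8 times in both. Direction and size are unknown for this trial. Reporting the covariance structure and degrees-of-freedom method alongside the package, which SAP 6.6 already undertakes to report, would let a reader judge the fit. No change to the plan is needed.
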